5.4 Adherence Assessment

Subjects are expected to take at least 2 doses of the assigned statin doses prior to their CEA.

In order to assess study drug compliance/safety, we will call the subjects on follow up Day 3 (+/-1 day), Day 7 (+/-1 day), and Day 10 (+/- 1 day) if the day of CEA has not yet occurred. The pre-CEA follow ups done per patient will be determined by their date of CEA. If the date of CEA occurs on or before a scheduled pre-CEA follow up, then those follow ups will not be done. If the CEA is done on the day of a follow up, the Day of CEA follow up will include the BLESSED ADL. The absence of a follow up as a result of following CEA will not be considered a deviation from protocol. The safety follow-up phone calls will begin based on when the study drug is scheduled to start or upon enrollment for Arm 1. We will collect the study drug bottle once the patient is admitted for their CEA to count any remaining capsules and also collect the Study Medication Compliance form (diary) completed by the subject attesting they took the doses and noting the reason(s) any dose was not taken.

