1.2 Secondary Objectives

- 1) To determine whether a pre-operative statin regimen alters the prevalence of early mortality at Day 365 +/- 30.
- 2) To determine whether differences in eCD/dCD identified in Primary Objectives 1- 4 are associated with either:
 - a. levels of, or peri-operative changes in, ESR/CRP, and/or
 - b. changes in either activities of daily living (BLESSED) or cognition (TICS-M) in the year following randomization and surgery.

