7.2 Specification of Safety Parameters

7.2.1 Protection Against Clinical Risks

Protection against other statin drugs being given to the subject participants prior to CEA:

- A letter for the subject's Primary Medical Doctor will be prepared to avoid duplication of prescribed statin doses or unknown changes to their statin regimen (see Appendix VI).
- Although extremely rare in FDA approved statin doses, the risks associated with statin use such as myalgias, arthralgias, gastrointestinal distress, or elevation in blood sugar can occur in some individuals.² Consequently, consented participants will first have various laboratory tests and assessed for clinical symptoms to assure safety. The laboratory tests conducted at baseline, Day of CEA, Day 1 post CEA (12-25 hours post-op) and 30 +/- 5 days post CEA or Day of post-op clinical visit. These include: CBC w/differential, comprehensive metabolic panel (which includes blood glucose levels, creatinine, and Hepatic LFTs), CK, and a lipid profile to detect any physiologic symptoms associated with the statin intervention.

¹ (<http://www.fda.gov/ForConsumers/ConsumerUpdates/ucm293330.htm>):

² (<http://www.fda.gov/ForConsumers/ConsumerUpdates/ucm293330.htm>):

- Abnormal lab results at baseline: anyone with elevated CK (5x > ULN) or LFTs (2x > ULN) will not be asked to take the study drug. These subjects will screen out from the study, and their future statin regimen will be determined by their treating physician. The blood draw will not be done fasting; however, anyone with abnormally high and uncontrollable blood glucose levels will also be screened out. All of the results will be reported to the subject participants via phone and advised to address abnormal results will become part of their medical record.
- Abnormal lab results on Day of CEA, Day 1 post CEA (12-25 hours post-op) and/or Day 30 +/- 5 days post CEA (or Day of PO clinical visit): anyone with elevated CK and LFTs will be considered an AE. Anyone with CK 5x > ULN with symptoms or 10x > ULN without symptoms and/or LFTs 2x > ULN with symptoms or 3x > ULN without symptoms will be considered a Serious Adverse Event. Also, their statin regimen will be determined by their treating physician who will be made aware of the abnormal findings. The results will also be in the patient's medical records and available for the treating physicians to address. We will continue to follow them for the remainder of the study to assess for safety.

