- We will report any abnormal laboratory values **not present at baseline** as adverse events. This will include abnormal laboratory values showing any potential acute kidney injury (AKI) defined as a serum creatinine increase of 50% from baseline within 7 days.³
- Clinical study assessments for statin intolerance will be done via phone using structured questionnaires to assess for safety/adverse events and compliance on:
 - Day 3 (+/-1d) if not preceded by CEA, 7 (+/- 1d) if not preceded by CEA, 10 (+/- 1d) if not preceded by CEA and Post-CEA: Day 7 (+/- 3d), Day14 (+/- 3d), Day 21 (+/- 3d), and Day 365 (+/- 30d)
- Clinical assessments for statin intolerance will be done in person while the patient is in the hospital for their CEA and during Day 30 +/- 5 days post-CEA or in-person the day of their post-CEA clinical visit.
- In addition, while the patient is in the hospital for the CEA, we will monitor the medical chart for any adverse events (clinical or laboratory based).

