7.2.2 Protection Against Other Minor Procedure/Study Related Risks

- It is expected that some individuals may feel uncomfortable taking cognitive tests; consequently, we will make every effort to ensure subject participant comfort during their neurocognitive testing.
- There will be three blood draws which could potentially produce minimal pain, bruising or discomfort; however, blood draws will be conducted by trained professionals which will minimize any of the above mentioned risks
- Every effort will also be made to ensure the confidentiality of the subject participant, including the use of unique patient identifiers for the study forms, and database entry. The subject binders/data

³ http://www.kdigo.org/clinical_practice_guidelines/pdf/KDIGO%20AKI%20Guideline.pdf

will be kept in a locked cabinet within a locked room which is only accessible to the study team. If any subject contact information is kept digitally, it will be kept in a password protected computer only accessible to authorized study personnel.

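### The schedule weakens Secondary Objective 2: no pre-dose TICS-M or BLESSED, no TICS-M for the earliest surgeries, and no early post-operative ESR/CRP

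*Combined protocol and SAP*

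**What the plan says.** Section 1.2 sets two parts for Secondary Objective 2. Part 2a concerns "levels of, or peri-operative changes in, ESR/CRP". Part 2b concerns "changes in either activities of daily living (BLESSED) or cognition (TICS-M) in the year following randomization and surgery".

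**TICS-M and BLESSED.** The baseline set in 6.2.3 is taken after randomization and before the first study dose. It lists the neuropsychometric battery, AMNART or WAT, CAM and blood tests, but neither of these two instruments. The Schedule of Assessments (6.1 and Appendix I), 6.2.5 and 6.2.6 place both at the Day 3 (±1) call and at Day 365 (±30). Day 3 counts from study drug start in Arms 2 and 3 and from enrollment in Arm 1.

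**Dropped calls.** Section 5.4 states: "If the date of CEA occurs on or before a scheduled pre-CEA follow up, then those follow ups will not be done". It then adds: "If the CEA is done on the day of a follow up, the Day of CEA follow up will include the BLESSED ADL". It gives no such rule for TICS-M, and says that a call lost this way is not a protocol deviation. Section 3 allows surgery after as few as 2 doses, and 7.1 expressly foresees surgery before Day 3.

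**Laboratory tests.** The Schedule and 6.2.5 give ESR and CRP at baseline, the day of CEA and Day 30. Section 7.2.2 agrees: "There will be three blood draws which could potentially produce minimal pain". Section 7.2.1 describes a further time point: "The laboratory tests conducted at baseline, Day of CEA, Day 1 post CEA (12-25 hours post-op) and 30 +/- 5 days post CEA".

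**The concern.** A change over the year needs a starting value. Here that value comes a few days after the assigned regimen begins in Arms 2 and 3, and patients operated on early do not get it at all for TICS-M. Lead time decides how many study doses a patient takes, so the missing values are concentrated at one end of the exposure range. The plan creates this loss when it is followed exactly.

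The protocol sees the need for a pre-dose measurement elsewhere: 6.2.4 takes the first neuropsychometric battery at enrollment to allow for effects of changing the statin. TICS-M and BLESSED were not treated the same way.

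For 2a, section 2.1.4 says ESR and CRP will follow acute as well as chronic inflammation. The scheduled draws leave the days just after surgery unmeasured. At stake are the precision and representativeness of 2b, and what 2a may claim about an acute response.

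**Working it through.** **Step 1. Time points (6.1, Appendix I, 6.2.3, 6.2.5, 6.2.6).**

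| Measure | Pre-dose baseline | Day 3 call | CEA day | Post-op Day 1 | Day 30 | Day 365 |
|---|---|---|---|---|---|---|
| TICS-M | no | yes | no | no | no | yes |
| BLESSED | no | yes | only under 5.4, if CEA falls on a follow-up day | no | no | yes |
| ESR, CRP | yes | no | yes | no | yes | no |

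The ESR/CRP row gives three draws, which reproduces the figure in 7.2.2. Draws after the day of surgery and before Day 30: 0. Pre-dose TICS-M or BLESSED: 0.

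**Step 2. Share without a pre-operative value.** The documents give no distribution of surgery dates. Assumption: CEA day *d* is uniform over the 17 days from 2 to 18 shown in the Schedule, on the same clock as the call, and the call is made on day *c* = 2, 3 or 4.

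- TICS-M under 5.4, lost if *d* ≤ *c*: 1/17 = 5.9%, 2/17 = 11.8%, 3/17 = 17.6%.
- BLESSED under 5.4, lost if *d* < *c*: 0%, 1/17 = 5.9%, 2/17 = 11.8%.
- Shorter lead times, call on Day 3, TICS-M: days 2–10 give 2/9 = 22%; days 2–7 give 2/6 = 33%.

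The sections differ on when the call is dropped. Section 5.4 drops it when surgery is on the same day or earlier. Section 6.2.5 and the Schedule footnote drop it only when surgery comes first. For a Day 3 call, that choice moves the TICS-M loss from 11.8% to 1/17 = 5.9%.

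**Step 3. Effect on precision.** The plan gives no power figure for Objective 2, so this is illustrative. Assumptions: N = 1,000, otherwise complete data, two-sided 0.05, 80% power, and eCD of 11% or 20% (the prior-cohort rates on and off statins in 2.2). The detectable difference in one-year change between patients with and without eCD, in SD units, is (1.960 + 0.842) × √(1/n₁ + 1/n₂).

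- eCD 11%, no loss: 2.802 × √(1/110 + 1/890) = 0.283.
- eCD 11%, 12% loss: 2.802 × √(1/96.8 + 1/783.2) = 0.302. At 33% loss: 0.346.
- eCD 20%: 0.221 with no loss, 0.236 at 12%, 0.271 at 33%.

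**Step 4. Laboratory passages side by side.** Section 7.2.1 has a Day 1 post-operative set. The Schedule, the Day 1 list in 6.2.5 and the three draws in 6.3 and 7.2.2 do not. The 7.2.1 panel is CBC, metabolic panel, CK and lipids, so even if it stands it holds no ESR or CRP. Section 7.1 refers to CEA-day laboratory values from the morning of surgery; 6.2.5 does not say on which side of surgery the second draw falls.

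**The case against.** A reader might infer that Objective 2 cannot be answered, or that no peri-operative change in ESR/CRP can be computed. The documents support neither. Part 2a is worded as levels or changes. Three draws give levels at each time point and changes among baseline, CEA day and Day 30. Part 2b can be analysed in every patient who has the call. Nor does every early patient lose BLESSED: 5.4 moves it to CEA day when the dates coincide, and the ±1 day window lets a Day 2 call precede a Day 3 operation.

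Other points against the concern also carry weight. The protocol never calls the Day 3 call a baseline, and it does fall after randomization, as 2b asks. Arm 1 takes no study drug, and Arm 2 controls take placebo on an unchanged statin. Nothing in the documents shows that a few doses alter TICS-M or BLESSED. Section 5.1 aims for early enrollment and as many doses as possible, which would reduce the loss. At 12% loss the cost in precision is small.

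The missing-data text in 9.1 offers a check for data missing completely at random, corrected estimates under missing at random, and non-ignorable sensitivity analyses. These methods can model the loss but not prevent it. The worked example regresses missingness on the outcome at baseline, which for TICS-M is the value that is absent.

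What remains is the lack of a pre-dose value, the unrecovered TICS-M, the missing early post-operative ESR/CRP, and the conflicts between sections.

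**Conclusion.** Secondary Objective 2 is weakened by the schedule, and the weakness is avoidable. One-year TICS-M change is missing by design for patients operated on by the day of the Day 3 call. That is about 12% if surgery day is uniform over days 2 to 18, 6% to 18% across the call window, and more if lead times are shorter. These shares rest wholly on the assumed timing. BLESSED is affected less. The main harm is selective loss among patients with few doses; the loss of precision is secondary. For 2a, the scheduled samples support levels and baseline, CEA-day and Day 30 changes, but not an early post-operative response.

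**What to change.** 1. Obtain TICS-M and BLESSED in all arms at the existing baseline visit in 6.2.3, or by telephone before dose 1. This costs a longer visit. An in-person first TICS-M may differ slightly in mode from the Day 365 call; a pre-dose telephone call avoids that.
2. Reconcile 5.4 with 6.2.5 and the Schedule footnote on whether the call is dropped when surgery falls on the same day. Reconcile the CEA-day BLESSED in 5.4 with the Schedule and the CEA-day list in 6.2.5, where it does not appear.
3. Reconcile the Day 1 laboratory tests in 7.2.1 with the Schedule, 6.2.5, 6.3 and 7.2.2. Adding ESR and CRP to a Day 1 draw would be a new procedure, because the 7.2.1 panel omits them. Unless the sponsor keeps that draw and chooses to add them, reword Objective 2a to levels and changes at baseline, CEA day and Day 30, and state whether the CEA-day sample is taken before surgery.

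Items 2 and 3 are text changes unless the sponsor opts for the extra tests.

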6 STUDY PROCEDURES

6.1 Schedule of Assessments

Procedure	STUDY DRUG TREATMENT PHASE				D2-D18	POST CEA FOLLOW UP PHASE					
	Baseline Dose 1	Day 3** +/- 1d	Day 7** +/- 1d	Day 10** +/- 1d		Day 1* (12-25 hours)	Day 7 (+/-3d)	Day 14 (+/-3d)	Day 21 (+/-3d)	Day 30 (+/-5d or PO Visit)	Day 365 (+/-30d)
Informed Consent	X										
Randomization	X										
Study Drug given to subject along with # of capsules to take per dose in the Study Medication Compliance form	X										
Concomitant Medications	X	Any other time the subject states he/she has had a change in medication									
Vitals (height/weight/BP from chart)	X				X	X				X	
Demographics	X										
Education	X										

Medical History (chart/interview)	X	Any other time the subject states he/she has had a change in medical status									
Tobacco Use	X										
Substance Use	X										
CAM	X				X	X				X	
MoCA/AD8 Screening	X										
AMNART or WAT	X										
Neuropsychological Tests (NPT)	X				X	X				X	
TICS-M		X									X
BLESSED ADL		X									X
Safety Questionnaire (CALL)		X	X	X			X	X	X		X
Safety Questionnaire (IN-PERSON)					X	X				X	
Pill Count					X						
CEA Details					X						
Neurological Exam post CEA (chart)					SOC	SOC					
EKG (from chart)	SOC				SOC						
Shipped Lab: ApoE (1x only)	At enrollment or during hospitalization(shipped as ambient blood Monday-Thursday)										
Site Lab: Comprehensive Metabolic Panel	X				X					X	
Site Lab: CK	X				X					X	
Site Lab: Lipid Profile	X				X					X	
Site Lab: CBC with differential	X				X					X	
Site Lab: ESR (Sedimentation Rate)	X				X					X	
Site Lab: C-Reactive Protein	X				X					X	
Site Lab: Urine Pregnancy or Beta-HCG ^A	SOC as part of pre-op labs ^A										
Assess for Adverse Events (AEs)		X	X	X	X	X	X	X	X	X	X
Procedure	STUDY DRUG TREATMENT PHASE					D2-D18	POST CEA FOLLOW UP PHASE				
	Baseline Dose 1	Day 3** +/- 1d	Day 7** +/- 1d	Day 10** +/- 1d	CEA DAY	Day 1* (12-25 hours)	Day 7 (+/-3d)	Day 14 (+/-3d)	Day 21 (+/-3d)	Day 30 (+/-5d or PO Visit)	Day 365 (+/-30d)
Study Completion/Discontinuation	At the end of the subject's participation										

*After surgery ends ** follow-up calls before CEA will be conducted only if not preceded by CEA ^A Urine Pregnancy test or Beta-HCG will be measured only in women of child-bearing age. SOC: Standard of Care v. 1-30-2018

6.2 Description of Evaluations

6.2.1 Consenting Procedure

The site's IRB protocol approval will state who is designated to consent potential participants. Study doctors and coordinators approved by the site's IRB will be permitted to facilitate the informed consenting process. All investigators need to be certified, by examination, in Good Clinical Practices and the Protection of Human Subjects. This study will be approved by the Institutional Review Board of the Columbia University Medical Center, as the coordinating site, and the IRBs of the other local centers.

The potential subject participant will be identified by the surgical/clinical team via the planned consultation to discuss undergoing a carotid endarterectomy. The potential subject participant will be informed about the study, once the potential subject expresses interest in knowing more about the study, the study coordinator and/or doctor will approach the individual and give them the opportunity to participate in this clinical trial. A copy of the consent form will be provided to them, in English or Spanish (whichever is their preferred language), and then the study personnel will facilitate the understanding of the study purpose, procedures and timeline of participation to allow them to make an informed decision about whether or not to participate in this clinical investigation. The information provided will include:

- the purpose and rationale of the study
- the clarification that this is an experimental process and not part of the current standard of care
- what their participation process and procedures will be during the study
- the duration of the study participation
- the expected risks and benefits
- the number of study participants expected and approved at the site and at other sites participating in this study
- understanding that they will not incur any additional costs to participate in this study
- clarification of whom they should contact if they experience any adverse reactions and also if they feel they have been harmed in any way due to their study participation
- discuss how confidentiality will be addressed and protected
- details of when a subject's participation may be screened out or considered an OUTCOME by the study investigator without regard to the subject's consent
 - If the MoCA (≤ 25 points) and the AD8 (≥ 2 points) - screen failure
 - If baseline laboratory results indicate existing hepatic or muscle abnormalities that would preclude potentially increasing or adding statins to their current medical regimen (CK $> 5 \times$ ULN and LFTs $> 2 \times$ ULN) – screen failure
 - If the subjects experience stroke or TIA peri-operatively, they will be considered as having reached a secondary OUTCOME in the study.
- explanation that participation is voluntary and that refusal to participate will not create any loss of benefits to which they would have otherwise received:
 - Including the clarification that they can discontinue their participation at any time without affecting their clinical treatment or any other right or benefits to which he/she is otherwise entitled.
 - Details of procedures expected for an orderly termination of the study participation by the individual

Once the study has been explained, the potential subject participants will be asked if they have any questions and given adequate amount of time to ask questions and/or discuss the study with family and friends to decide whether they should participate.

This process will allow sufficient opportunity for the potential participants to provide voluntary, informed consent to participate (or not) and know that they can withdraw at any time without any undue influence or coercion. All participants who consent will be given a copy of the informed consent form for their records and the original consent form will be filed in their study subject binder.

Subjects must provide individual informed consent before any screening tests are performed. When a subject signs the Informed Consent Form (ICF), the subject is considered consented, but not enrolled until they pass the complete screening process for MCI and hepatic/muscle abnormalities (see 6.2.1). Then and only then will they be assigned/randomized to a study arm. The study personnel consenting the subject participant must also sign and date the ICF.

6.2.2 Screening Evaluation

The screening evaluations for MCI and hepatic and muscle testing will be completed after consent and prior to randomization in the study. The screening assessments must be completed prior to the subjects CEA such that the minimum of 2 doses (maximum of 18) are taken. The screening assessments are:

- MoCA
- AD8
- Laboratory (LFTs & CK)

All potential participants will be pre-screened for eligibility by reviewing patient chart and speaking with the patient regarding the inclusion/exclusion criteria prior to offering them participation and informed consent. The final screening process for participation will be after they have consented to participate in order to screen those who may already have mild cognitive impairment (MCI) from the study. The participants who provide informed consent will be screened for MCI by administering the MoCA (≤ 25 abnormal) and the AD8 questionnaire (≥ 2 abnormal). If both assessments are not within normal ranges, these patients will not be randomized or assigned to the observational arm. Those with baseline MCI will be screened out from the study and not followed.

- **MoCA (Montreal Cognitive Assessment):** The MoCA is a global cognitive screening test with favorable psychometric properties (69, 70); it has been shown to be more sensitive to executive impairment than the Mini-Mental State Examination (MMSE). (75) It screens 8 domains: visuospatial/executive, naming, memory, attention, language, abstraction, delayed recall, and orientation. The assessment takes approximately 10 minutes. The highest possible total score is 30 points, and the assessment is available in various languages, including Spanish.
- **AD8 (Eight-item Informant Interview to Differentiate Aging and Dementia):** A screening test in itself is insufficient to diagnose a dementing disorder. The AD8 is, however, quite sensitive to detecting early cognitive changes associated many common dementing illness including Alzheimer disease, vascular dementia, Lewy body dementia and frontotemporal dementia. (72) This will serve

as a preliminary screen for MCI by asking the patient if they have noted any memory loss in spite of having normal ADLs (65).

- **Laboratory Screening:** Blood Draw #1 will include testing for Liver Function Test (LFTs) and Creatine Kinase (CK). If the baseline laboratory results indicate existing hepatic or muscle abnormalities that would preclude potentially increasing or adding statins to their current medical regimen (CK >5X ULN and LFTs > 2X ULN), this will also constitute a screen failure and the subject will be informed and considered a screen failure.

Participating study sites are required to document all screened candidates considered for inclusion in this study. If a subject is excluded from the study, the reasons for exclusion must be documented in the screening log (Appendix III) and the subject's file folder containing his signed consent form. The screening logs will be collected monthly by the Central Coordinating Center at CUMC.

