11.2 Informed Consent Forms

The potential subject participant will be identified by the surgical/clinical team via the planned consultation to discuss undergoing a carotid endarterectomy within. The potential subject participant will be informed about the study, once the potential subject expresses interest in knowing more about the study, the study coordinator and/or doctor will approach the individual and give them the opportunity to participate in this clinical trial. A copy of the consent form will be provided to them, in English or Spanish (whichever is their preferred language), and then the study personnel will facilitate the understanding of the study purpose, procedures and timeline of participation to allow them to make an informed decision about whether or not to participate in this clinical investigation. The information provided will include:

- the purpose and rational of the study
- the clarification that this is an experimental process and not part of the current standard of care
- what their participation process and procedures will be during the study
- the duration of the study participation
- the expected risks and benefits
- the number of study participants expected and approved at the site and at other sites participating in this study
- understanding that they will not incur any additional costs to participate in this study
- clarification of whom they should contact if they experience any adverse reactions and also if they feel they have been harmed in any way due to their study participation
- discuss how confidentiality will be addressed and protected

- details of when a subject's participation may be screened out or considered an OUTCOME by the study investigator without regard to the subject's consent
 - If the MoCA (≤ 25 points) and the AD8 (≥ 2 points) - screen failure
 - If baseline laboratory results indicate existing hepatic or muscle abnormalities that would preclude potentially increasing or adding statins to their current medical regimen (CK $> 5 \times$ ULN and LFTs $> 2 \times$ ULN) – screen failure
 - If the subjects experience stroke or TIA peri-operatively, they will be considered as having reached an OUTCOME in the study.
- explanation that participation is voluntary and that refusal to participate will not create any loss of benefits to which they would have otherwise received:

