 - Including the clarification that they can discontinue their participation at any time without affecting their clinical treatment or any other right or benefits to which he/she is otherwise entitled.
 - Details of procedures expected for an orderly termination of the study participation by the individual

Once the study has been explained, the potential subject participants will be asked if they have any questions and given adequate amount of time to ask questions and/or discuss the study with family and friends to decide whether they should participate.

This process will allow sufficient opportunity for the potential participants to provide voluntary, informed consent to participate (or not) and know that they can withdraw at any time without any undue influence or coercion. All participants who consent will be given a copy of the informed consent form for their records and the original consent form will be filed in their study subject binder.

Subjects must provide individual informed consent before any screening tests are performed. When a subject signs the Informed Consent Form (ICF), the subject is considered consented, but not enrolled until they pass the complete screening process for MCI and hepatic/muscle abnormalities (see 6.2.1). Then and only then will they be assigned to a study arm.

In a separate consent form, the participants will be given the opportunity to allow the surplus blood samples obtained from the study to be used in Future Research. This is not required to participate in the main study. If they agree, their surplus samples will be stored at CUMC for future research use. If they do not consent to Future Research, any remaining samples will be destroyed after the study analysis have been completed.

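### The CK/LFT baseline safety screen joins its limits with *and* in 6.2.1, 6.2.2 and 11.2 but with *or* in 7.2.1, and 6.2.3 places its only blood sample after randomisation

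*Combined protocol and SAP*

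**What the plan says.** **The limits.** Section 6.2.2 describes a laboratory screen for "existing hepatic or muscle abnormalities that would preclude potentially increasing or adding statins to their current medical regimen" and then gives the limits: "CK >5X ULN and LFTs > 2X ULN), this will also constitute a screen failure". Sections 6.2.1 and 11.2, in their lists of what patients are told at consent, print the same joint condition ("CK $> 5 \times$ ULN and LFTs $> 2 \times$ ULN"). Section 7.2.1 says instead that "anyone with elevated CK (5x > ULN) or LFTs (2x > ULN) will not be asked to take the study drug", and adds that such subjects leave the study at screening. The exclusion criteria in 4.2 contain no CK or LFT limit.

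**The order.** Section 6.2.2 states: "The screening evaluations for MCI and hepatic and muscle testing will be completed after consent and prior to randomization in the study". It names Blood Draw #1 as the source of the CK and LFT values. Section 6.2.1 makes passing the cognitive and hepatic/muscle screen a condition of entry: "Then and only then will they be assigned/randomized to a study arm". Section 11.2 repeats it: "Then and only then will they be assigned to a study arm". Section 7.2.1 says that "consented participants will first have various laboratory tests and assessed for clinical symptoms to assure safety".

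Section 6.2.3 gives a different order. Its baseline list includes Blood Draw #1, with CK and the metabolic panel that contains the LFTs. It times that list after both screening and randomisation, though before the first dose. Its randomisation text repeats the sequence: randomise, complete the baseline assessments, obtain the drug from pharmacy and hand it over. It also allows at most 15 minutes for the screening step.

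**The concern.** This is the laboratory safety gate before a statin is started or its dose raised. It can do that job only if every site applies the same limits and has the result in hand before assigning treatment. The protocol states both elements in conflicting ways.

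If a site takes the bracket in 6.2.2 at face value, a patient with a high CK and normal LFTs, or the reverse, does not meet the printed failure condition, although 7.2.1 screens that patient out. If a site works through 6.2.3 in order, the patient is randomised before the sample is drawn. Either route can leave a site with a randomised patient whom 7.2.1 bars from study drug. The protocol does not say how that patient should then be followed and analysed.

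**Working it through.** The protocol states no figure on this point, and no arithmetic applies. The check sets the statements side by side.

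**Step 1: are the two rules the same rule?** The limits (5 times ULN for CK, 2 times ULN for LFTs), the occasion (baseline) and the consequence (screen failure) are the same in 6.2.1, 6.2.2, 11.2 and 7.2.1. Only the connective differs.

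**Step 2: where do they disagree?** There are four possible results:

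| CK above limit | LFTs above limit | *and* (6.2.1, 6.2.2, 11.2) | *or* (7.2.1) |
|---|---|---|---|
| yes | yes | fails | fails |
| yes | no | does not fail | fails |
| no | yes | does not fail | fails |
| no | no | does not fail | does not fail |

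The rules differ in the two middle rows, that is, for every patient with exactly one value over its limit.

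**Step 3: which is intended?** The introductory phrase in 6.2.2 speaks of a hepatic *or* a muscle abnormality, and 7.2.1 says *or* outright. Both point to *or*. Section 4.2, where a site would look for an exclusion limit, is silent.

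**Step 4: can both orders hold?**

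- 6.2.1, 6.2.2 and 11.2: consent, then the CK/LFT result from Blood Draw #1, then assignment.
- 6.2.3: consent, then screening, then randomisation, then Blood Draw #1.

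Both could hold only if an earlier sample supplied the screen. Sections 6.3 and 7.2.2 each give three blood draws. Section 6.2.5 puts the second on the day of surgery and the third at Day 30. Section 7.2.1 also mentions laboratory tests on the day after surgery, which the schedule does not show, but that would be a later sample. No earlier one is scheduled, so the two orders cannot both be followed.

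**Step 5: does other text settle the order?** No.

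- The schedule in 6.1 puts consent, randomisation, drug supply and laboratory tests in one baseline column.
- Section 4.3 goes from the cognitive screen to randomisation without mentioning laboratory results.
- The 15-minute allowance in 6.2.3 suits the MoCA and AD8. It does not obviously allow for drawing, running and reviewing a blood sample.
- The deviation codes in Appendix IV treat randomisation before the baseline assessment is complete as an eligibility deviation, yet 6.2.3 prescribes that sequence.

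**The case against.** The best defence is that a careful site would get this right. The bracket can be read as one limit per organ, CK for muscle and LFTs for liver, under a phrase that already says *or*. Section 6.2.2 gives a condition that leads to failure; nowhere does the protocol say that an isolated elevation passes. Section 7.2.1 is itself an express screening rule, and a site that follows it also satisfies 6.2.2. On timing, three sections require the laboratory screen before assignment, and 6.2.3 says that patients are randomised once they have passed screening. On this view the fault is one list item that should have been split.

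Most of this stands as evidence of intent, and it rules out a reading that a reader might be tempted to draw: that the protocol authorises study drug for a patient with one isolated elevation. Section 7.2.1 forbids that. What remains is that the limits printed in the screening section itself say *and*, and that the section sites use to sequence enrolment puts the only available sample on the wrong side of randomisation. Inferring the right rule from other sections does not ensure that every site applies it.

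A reader might also infer a separate contradiction between screening out, safety follow-up and intention to treat. The documents do not support that as a free-standing conflict. It arises only if a site acts on the literal *and* or on the order in 6.2.3. The follow-up to Day 365 in section 8 covers patients who discontinue treatment, not those who never start it. The statement in 6.2.2 that patients are not followed concerns mild cognitive impairment only.

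**Conclusion.** The inconsistency is real in both parts. The CK/LFT rule is printed two ways that disagree for any patient with exactly one value over its limit, with *or* the evident intent. The order in 6.2.3 puts Blood Draw #1 after randomisation, although 6.2.1, 6.2.2 and 11.2 require its result before assignment.

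The size cannot be given as a count. The documents state no frequency of CK or LFT elevation in this population, and the planned enrolment figures do not measure the defect. The drug-exposure aspect concerns Arms 2 and 3, since Arm 1 receives no study drug.

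Two stronger conclusions should not be drawn. The first is that the analysed set would differ between sites: 9.1 and 9.5 fix intention to treat for all analyses, and the sites are given no choice of analysis set. The second is that the treatment comparison is biased: 6.2.3 places Blood Draw #1 before the first dose and Arms 2 and 3 are double-blind, so an exclusion on that sample would not reflect a treatment effect.

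The conclusion rests on reading the limits in 7.2.1 as the same as those in 6.2.2, and on there being no earlier sample beyond those the protocol schedules.

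**What to change.** - **Sections 6.2.1, 6.2.2 and 11.2:** write the limit as CK >5x ULN *or* LFTs >2x ULN, to match 7.2.1.
- **Section 6.2.3:** move the CK/LFT part of Blood Draw #1 to screening, require a reviewed result before assignment or randomisation, and limit the 15-minute statement to the MoCA and AD8.
- **Section 7.2.1, as a safeguard:** state that a patient found to fail only after randomisation takes no study drug but is followed to Day 365 and kept in the intention-to-treat analysis. This agrees with 7.1, which keeps patients with modified regimens under intention to treat, and with 9.1 and 9.5.

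The cost is amendment wording, including the consent-information lists. Randomisation would wait for a local laboratory result, and patients enrolled close to surgery may lose some of their 2 to 18 doses. That wait is already implied by 6.2.1 and 6.2.2.
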